2.1 INCLUSION CRITERIA

- 1. Patients with a pre-operative Knee Society Assessment Score of <70
- 2. Patients undergoing primary partial knee arthroplasty as unilateral arthroplasty or bilateral arthroplasty, simultaneously or otherwise

- 3. Patients diagnosed with osteoarthritis or avascular necrosis limited to the medial compartment of the operative knee joint
- 4. Male or female patients who are at least 21 years of age at the time of surgery
- 5. Patients with full thickness cartilage loss, with or without bone loss in the medial compartment
- 6. Patients with functionally intact ACL and PCL
- 7. Patients who need to obtain relief of pain and/or improved function in their knee
- 8. Patients with fixed flexion deformity < 15°
- 9. Patients who are able to follow post operative care instructions
- 10. Patients who are willing and able to return for scheduled follow-up evaluations
- 11. Patients in which natural alignment can be restored
- 12. Patients who have completed a valid, IRB approved Informed Consent Form
- 13. Patients with child bearing potential who voluntarily agree to prevent pregnancy for 2 years following device implantation

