2.4 INSTITUTIONS

A maximum of 12 investigational sites will enroll patients into the study.

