3.0 STATISTICAL ANALYSIS PLAN

This is a two-group, multi-center, randomized clinical trial to compare Biomet's cemented Oxford® Partial Knee System to another active intervention, the Oxford® Cementless Partial Knee System (abbreviations: Control vs. Cementless). Imbalanced, blocked randomization (2:1, Cementless vs. Control) will be implemented.

Randomization will be per patient. In the event that an intraoperative screen failure occurs post-randomization, randomization will not be reassigned and this patient will not count toward the overall sample size. Randomization will continue with the next subject enrolled as previously described. The randomization plan will be produced using SAS v 9.2 for Windows. Randomization will be by center, and each site will receive separate randomization plans using a predetermined block size that will remain undisclosed to the sites. The randomization assignments will be in the form of envelopes to be opened intra-operatively after the first tibial cut and bone quality is assessed against the eligibility criteria.

The primary study endpoint will consist of four (4) individual co-primary endpoints, including both safety and efficacy measures. The following endpoints are included as individual parts of the primary endpoint:

- 1. Knee Society Assessment Score number of points received for the Knee Society Assessment Score at the 22+ month assessment
- 2. Knee Society Function Score number of points received for the Function Score at the 22+ month assessment.
- 3. Revisions or removals of any component of the device or an unanticipated, device-related adverse event (UADE) at any time point. This is a binary endpoint in which a knee is either a "success" or "failure". To obtain a successful result, a knee must reach the 22 + month upper window limit with the device intact and without a component revision/removal or a UADE.
- 4. Radiographic Assessments at the 22+ month assessment

This is a binary endpoint in which a knee is either a "success" or "failure". To obtain a successful radiographic endpoint, a knee must meet the following criteria at the 22+ month

- a. Absence of osteolysis
- b. No migration/subsidence of any femoral or tibial component
- c. Absence of fractured component

Conversely, a radiographic failure is defined as follows:

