3.2. CALCULATION OF THE PRIMARY STUDY ENDPOINT

The confidence intervals used in the analysis of the binary primary endpoints (Radiographic Success and Absence of Revision/UADE) will be 1-sided, 95% confidence intervals for the difference between proportions in two independent samples. They will be calculated using the Wald method as based on a normal approximation to the binomial, as follows:

$$(p_C - p_I) + z_\alpha \sqrt{SE_C^2 + SE_I^2}$$

Where

^d As agreed at FDA pre-submission meeting **Q160425** April 13, 2016.

 p_C = proportion of success in the Control group,

p_I = proportion of success in the Investigational group,

 $\alpha = 0.05$, and

$$SE_C = \sqrt{\frac{p_C(1-p_C)}{n_C}}$$
 and $SE_I = \sqrt{\frac{p_I(1-p_I)}{n_I}}$

The confidence interval used in the analysis of the continuous primary endpoints (Knee Society Function and Assessment Scores) will be 95% confidence intervals for the difference between means in two independent samples. They will be calculated using the normal distribution, as follows:

$$(\bar{x}_C - \bar{x}_I) + z_\alpha \sqrt{\frac{s_C^2}{n_C} + \frac{s_I^2}{n_I}}$$

Where

 $\overline{x_C}$ = proportion of success in the Control group,

 $\overline{x_i}$ = proportion of success in the Investigational group,

 s_C = standard deviation for the Control group,

 s_{I} = standard deviation for the Investigational group,

and

 $\alpha = 0.05$

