3.3 SAMPLE SIZE JUSTIFICATION

In order to calculate the sample size for this study, the sample size needed to obtain 90% power for each primary endpoint was calculated. The endpoint requiring the largest sample size to maintain 90% power was Radiographic Success. Therefore, this is the sample size used in this study to ensure that we have a sufficient number of knees/patients to test each of the four primary endpoints with at least 90% power.

The sample size for the radiographic success primary endpoint was calculated as follows:

Let p_I and p_C denote the true population proportions of a successful outcome in the Cementless and Control groups, respectively.

Under H_0 , p_C is markedly larger than p_I and the Cementless device is inferior. Contrarily, under H_1 , this is not true and the true proportion of success for the Cementless device is, at worst, δ less than for the Control. We have δ = 0.08 (i.e., 8%).

Information about plausible values of the proportions p_I and p_C is available in the SSED for the LPS Flex Mobile Device (PMA #P060037). This document was used to help estimate the percentage of radiographic success for sample size purposes because it used a similar radiographic success/failure endpoint as the one given in this protocol. For purposes of the sample size calculation, we use the radiographic failure rates in Table 5 (page 18-19) of the document. This shows a 1.2% radiographic failure rate for the investigational device and a 2.4% radiographic failure rate for the control. Since we have slightly different radiographic success criteria, and because we want to ensure that we have adequate power for testing this endpoint, we will use 5% as our estimate of radiographic failure, giving a 95% estimate of radiographic success.

Assuming 95% to be the true, equal values of p_1 and p_2 , non-inferiority sample size calculations were implemented in nQuery Advisor 7.0 software using a 2:1 ratio of Cementless to Control subjects. This software uses methodology as described in an article by Farrington and Manning^e.

Definitions:

 p_l : Proportion of successes in the Experimental (Oxford Cementless) treatment group.

 $p_{\mathcal{C}}$: Proportion of success in the Control (Oxford Cemented) treatment group.

For a specified constant, $0 < \delta < 1$, the hypotheses of non-inferiority are:

$$H_0: p_C - p_I > \delta \text{ vs. } H_1: p_C - p_I \leq \delta.$$

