3.5 ANALYSIS OF STUDY DATA

3.5.1. DESCRIPTIVE STATISITICS INCLUSING PATIENTS' BASELINE STATUS

Subjects in the Cementless and Control groups will be compared regarding a list of baseline items, including Knee Society Assessment and Function Scores, demographics (age, gender), medical history, unilateral vs. bilateral status, and use of pain medication for knee-related and non-knee related issues. Standard statistical tests (chi-square, Cochran-Mantel-Haenszel chi-square, Student's t) will be used.

Equitable numbers of men and women are expected to be enrolled. Therefore, we will not perform a stratified analysis for the primary endpoint or stratify randomization on this variable. However, the proportions of males and females in each group will be summarized and compared as stated above in the analysis of baseline data. In addition, the effect of gender on the primary outcomes at 24 months will be assessed within either a linear regression (for continuous primary endpoints) or logistic regression model (for binary primary endpoints) as described below in the Exploratory Analysis section.

Because this is a randomized study, baseline characteristics are expected to be similar between the two treatment groups. If this is not the case based on statistical tests conducted above, then sensitivity analyses will be conducted to assess the impact of the baseline variable in question on study success. In addition, the effect of the baseline variable in question will be assessed within a linear or logistic regression model as described below in the Exploratory Analysis section.

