3.5.5. MISSING DATA, SENSITIVITY ANALYSES AND ACCOUNTABILITY TABLES

Data will be considered "missing" for a given primary endpoint if this endpoint cannot be calculated or is not available for a subject. If the subject has had a device failure or a UADE at any point or prior to their 22+ month outcome, they will not be considered as missing data for the Absence of Revision/Removal/UADE endpoint, as this endpoint is cumulative. A subject who has had a revision prior to two years will be considered a radiographic failure at the two - year time point for purposes of the primary analysis. When possible (i.e. the subject is seen by a study investigator in a non-emergency situation and collection of the data will not cause undue burden), Knee Society Scores will be collected for these subjects before the revision is performed in order to prevent these patients from missing knee scores in the primary efficacy analyses. A "worst case" score of twelve will be given for any Knee Scores that cannot be collected prior to the revision procedure. As an attempt to minimize missing data from the remaining primary endpoints, a nextobservation-carried-backward approach will be used to impute values for subjects missing data. Under this approach, if a primary endpoint is missing at the 24 month visit, the subject's next observation post 24-months will be used to impute a 22+ month outcome for that subject, for that particular endpoint. If no data is available after 2 years to carry backward for the missing data point, the subject's latest observation pre-24months will be carried forward to impute values for the missing 24 month visit.

Sensitivity analyses will examine the sensitivity of the results to missing values of the primary outcomes using a tipping point analysis, a best-case analysis, a worst-case analysis, and an analysis that imputes missing data with the last observation carried forward. If sensitivity analyses do not agree and we have more than 15% of values missing in either group, the method of Multiple Imputation may be used to further investigate the sensitivity of results to the missing data.

Accountability tables will be generated to show, at each study visit, the number of subjects who might be expected to attend a given visit and the number and proportion who did attend. Rows of the table will show counts for subjects contributing all data needed to

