Patient covariates in the proposed statistical modeling below include age at time of surgery, gender, primary diagnosis, unilateral vs. bilateral status, preoperative Knee Society Assessment Scores, Knee Society Function Scores, use of pain medications and study site. Others may be added if other covariates potentially affecting the outcome are observed. To determine the effect of these covariates on the primary endpoints, separate regression models will be used. In the regression models, the dependent variable will be the primary study endpoint; thus a logistic regression model will be needed for the binary study endpoints. The model will also include device group (control or experimental) as an independent variable and the above baseline and demographic variables listed above as covariates. A graphical examination of the residuals will be performed to assess the model assumptions. To determine whether a covariate has an effect on the primary study outcomes, a Type 3 analysis of effects based on the Wald Chi-square test will be conducted.

^f Gail, M.H., and Simon, R. "Testing for qualitative interactions between treatment effects and patient subsets." *Biometrics*, 1985, **41**, 361-272,

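### The deciding interval for the two Knee Society co-primaries uses neither the pre-operative score nor the randomization center, and so forgoes a modest gain in precision

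*Combined protocol and SAP*

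**What the plan says.** Sections 3.1.3 and 3.1.4 decide non-inferiority on the upper limit of a one-sided 95% interval for Control minus Cementless, with margins of 6.4 points (Assessment) and 9.2 points (Function). Section 3.2 gives the formula. The intervals "will be 95% confidence intervals for the difference between means in two independent samples": the raw difference in means plus a normal quantile times a standard error built from each group's own SD. There is no covariate.

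The information for an adjusted analysis exists:

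- Section 3.0: "Randomization will be by center, and each site will receive separate randomization plans". Section 2.4: "A maximum of 12 investigational sites will enroll patients into the study".
- The Knee Society form is scheduled pre-operatively (2.7.1) and must be approved before the study components are released (2.7). Section 3.5.1 lists both scores as baseline items.
- Section 3.5.6 names as covariates "preoperative Knee Society Assessment Scores, Knee Society Function Scores, use of pain medications and study site", but only in exploratory regressions.
- On baseline similarity of the groups, Section 3.5.1 says: "If this is not the case based on statistical tests conducted above, then sensitivity analyses will be conducted".
- Section 3.5.6 also allows a stratified analysis by site, but only if an interaction test prompts it and it is thought necessary.

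None of these analyses supplies the bound that decides study success.

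**The concern.** The design blocks on center, and the plan treats baseline score and site as possibly prognostic, yet the deciding analysis uses neither. Any outcome variance they explain stays in the standard error. Chance imbalance in the pre-operative score stays in the point estimate, and is looked at only through sensitivity or exploratory work.

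Section 3.1 requires all four co-primaries to pass, so avoidable width on one of them lowers the chance of overall success a little. The Assessment score is the more exposed of the two because its margin is tighter.

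**Working it through.** **The plan's own figure.** The stated 191 vs 96 is driven by radiographic success (95% in both groups, margin 0.08, one-sided 5%, power 90%, 2:1). With unpooled variance, Control n = 0.95 × 0.05 × 1.5 × (1.645 + 1.282)² / 0.08² = 95.3, so 96, and Cementless is 190.7, so 191. Inflation also reproduces: 191/0.75 = 254.7 (255) and 96/0.75 = 128.

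**What the power claim implies for the SDs.** No SD is given for either knee score. Section 3.3 says that radiographic success needed the largest sample and that this size is enough "to test each of the four primary endpoints with at least 90% power". With k = √(1/191 + 1/96) = 0.1251, the largest SD compatible with 90% power is:

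- Assessment: 6.4 / (0.1251 × 2.926) = 17.5
- Function: 9.2 / (0.1251 × 2.926) = 25.1

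These are ceilings, not estimates.

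**Gain from the pre-operative score.** Let r be the assumed correlation between the pre-operative and 22+ month scores. Adjustment multiplies the half-width by √(1 − r²). With true difference zero, power = Φ(margin / (SD × k × √(1 − r²)) − 1.645).

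| r | Half-width reduction | Half-width, SD 17.5 | Assessment power, SD 17.5 | Assessment power, SD 15 |
|---|---|---|---|---|
| 0 (unadjusted) | – | 3.60 | 89.9% | 96.1% |
| 0.1 | 0.5% | 3.58 | 90.2% | 96.3% |
| 0.2 | 2% | 3.53 | 91.0% | 96.7% |
| 0.3 | 5% | 3.44 | 92.2% | 97.3% |
| 0.5 | 13% | 3.12 | 95.8% | 98.9% |

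Entry is limited to "Patients with a pre-operative Knee Society Assessment Score of <70". This restricts the baseline Assessment range and makes the lower values of r more plausible for that score. For r of 0.1 to 0.3 at SD 17.5 the gain is about 0.3 to 2.3 points of power.

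For Function, unadjusted power is 99.5% at SD 17.5, so there is nothing to gain. At SD 25 it is 90.3%, rising to 91.3% (r = 0.2) or 92.5% (r = 0.3).

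**Effect of ignoring center.** If site explains a share ICC of the variance, blocking within site removes that share from the true variance of the difference, but the unadjusted standard error still counts it. The actual one-sided level is 1 − Φ(1.645 / √(1 − ICC)): 0.050, 0.046 and 0.041 at ICC of 0%, 5% and 10%. The unadjusted test is conservative, never liberal, on this account.

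**Which standard error.** Section 3.2 now uses separate group variances, and an adjusted analysis should not give that up. Section 3.5.5 says that a worst-case "score of twelve will be given for any Knee Scores that cannot be collected prior to the revision procedure", which could make the variances differ. With assumed SDs of 20 (Control) and 15 (Cementless):

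- correct SE = √(400/96 + 225/191) = 2.312
- pooled SD = √((95 × 400 + 190 × 225)/285) = 16.83, so pooled SE = 16.83 × 0.1251 = 2.106
- ratio 0.911, giving an actual level of 1 − Φ(1.645 × 0.911) = 0.067

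**Simulation** (10,000 runs, 12 sites of 24 patients, blocks of 6 at 2:1, r = 0.2 unless stated):

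| Scenario | Unadjusted | Pooled ANCOVA | Adjusted, HC2 |
|---|---|---|---|
| Type I error, SDs 20/15, no site variance | 0.048 | 0.062 | 0.047 |
| Type I error, SDs 20/15, 5% site variance | 0.044 | 0.068 | 0.050 |
| Power, SD 17.5, no site variance | 90.4% | – | 91.2% |
| Power, SD 17.5, 5% site variance | 90.3% | – | 91.9% |
| Power, r = 0, no site variance | 90.1% | – | 90.0% |

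If the covariates turn out useless, about 0.1 point of power is lost in this run.

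**The case against.** The strongest reply is that nothing is broken. A pre-specified two-sample interval in a randomized trial is a legitimate choice, its standard error already allows for chance imbalance, and the plan does examine these covariates elsewhere. That stands, and it is why the point is minor.

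The size of the gain is wholly assumed, and SD 17.5 is the least favorable value the plan allows. This also stands. At SD 15 the Assessment gain for r of 0.1 to 0.3 is about 0.1 to 1.2 points from 96.1%. At SD 12 power is already 99.6%. For Function at SD 20 it goes from 97.9% to between 98.0% and 98.6%.

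The evaluable number may exceed 191/96, because Section 3.5.5 imputes missing 22+ month scores from a later or earlier visit. If only the 10% bilateral allowance is lost (0.9 × 255 ≈ 230 and 0.9 × 128 ≈ 115, an assumption), Assessment power at SD 17.5 is 94.0% unadjusted and 94.2%, 94.8% or 95.7% at r = 0.1, 0.2 or 0.3. The gain shrinks to about 0.2 to 1.6 points but does not vanish. The 191/96 used above is the plan's own evaluable size.

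Finally, the trial is under way with single blinding only, and changing a deciding estimator mid-study could raise a credibility question. That is a real constraint on timing. It is met by fixing the change before any comparative outcome data are seen, leaving the margins alone and still reporting the present interval. Radiographic success, which sets the sample size, is unaffected either way.

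**Conclusion.** The point holds as a minor efficiency improvement. The deciding intervals for both knee scores omit a prognostic baseline measure that is already collected and the factor used to block randomization. They remain valid, and no power shortfall is shown.

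For the Assessment score the realistic gain is up to about 2 points of power near the SD ceiling of 17.5, and less at smaller SDs. A correlation of 0.5 would bring about 6 points, but the entry cap makes that less likely. Function benefits only if its SD is near 25. All of this depends on assumed values of SD, r and site variance, which the documents do not give.

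**What to change.** In Sections 3.1.3, 3.1.4 and 3.2, pre-specify the following, irrespective of any baseline test and before comparative outcome data are seen:

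> Non-inferiority on each Knee Society score will be based on the Control minus Cementless difference from a linear model of the 22+ month score on treatment, the same pre-operative score and site (small sites pooled as in 3.5.1), with an HC2 heteroscedasticity-robust standard error. The one-sided 95% upper bound will be compared with 6.4 (Assessment) and 9.2 (Function).

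Keep the present Section 3.2 interval as a sensitivity analysis. Do not use the ordinary pooled-variance ANCOVA standard error, which under 2:1 allocation is too small if Control is the more variable group. The text should also name the reference distribution for the bound (keeping the normal quantile of 3.2 would be consistent) and say what is done if a pre-operative score is missing, which should be rare because the form is approved before surgery.

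The cost is a plan amendment with whatever approvals Section 2.13 requires. There are no new visits, forms or patients, and the sample size does not change. Up to 12 sites use about 12 degrees of freedom out of about 287 patients.

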3.3 SAMPLE SIZE JUSTIFICATION

In order to calculate the sample size for this study, the sample size needed to obtain 90% power for each primary endpoint was calculated. The endpoint requiring the largest sample size to maintain 90% power was Radiographic Success. Therefore, this is the sample size used in this study to ensure that we have a sufficient number of knees/patients to test each of the four primary endpoints with at least 90% power.

The sample size for the radiographic success primary endpoint was calculated as follows:

Let p_I and p_C denote the true population proportions of a successful outcome in the Cementless and Control groups, respectively.

Under H_0 , p_C is markedly larger than p_I and the Cementless device is inferior. Contrarily, under H_1 , this is not true and the true proportion of success for the Cementless device is, at worst, δ less than for the Control. We have δ = 0.08 (i.e., 8%).

Information about plausible values of the proportions p_I and p_C is available in the SSED for the LPS Flex Mobile Device (PMA #P060037). This document was used to help estimate the percentage of radiographic success for sample size purposes because it used a similar radiographic success/failure endpoint as the one given in this protocol. For purposes of the sample size calculation, we use the radiographic failure rates in Table 5 (page 18-19) of the document. This shows a 1.2% radiographic failure rate for the investigational device and a 2.4% radiographic failure rate for the control. Since we have slightly different radiographic success criteria, and because we want to ensure that we have adequate power for testing this endpoint, we will use 5% as our estimate of radiographic failure, giving a 95% estimate of radiographic success.

Assuming 95% to be the true, equal values of p_1 and p_2 , non-inferiority sample size calculations were implemented in nQuery Advisor 7.0 software using a 2:1 ratio of Cementless to Control subjects. This software uses methodology as described in an article by Farrington and Manning^e.

Definitions:

 p_l : Proportion of successes in the Experimental (Oxford Cementless) treatment group.

 $p_{\mathcal{C}}$: Proportion of success in the Control (Oxford Cemented) treatment group.

For a specified constant, $0 < \delta < 1$, the hypotheses of non-inferiority are:

$$H_0: p_C - p_I > \delta \text{ vs. } H_1: p_C - p_I \leq \delta.$$

Type I error: conclude that the difference p_C - p_I is less than δ when in fact the difference is greater than or equal to δ , *i.e.* conclude that the experimental treatment is non-inferior to the control treatment when the control treatment is actually substantially better.

Statistics in Medicine 9(1990) pp 1447-1454.

^eFarrington and Manning

[&]quot;Test statistics and sample size formulae for comparative binomial trials with null hypotheses of non-zero risk difference for non-unity relative risk".

Type II error: conclude that the difference is greater than or equal to δ when it is actually less than δ , *i.e.*, conclude that the experimental treatment is inferior to the control treatment when the experimental treatment is essentially just as good.

Assumptions:

$\alpha = 0.05$	Probability of Type I error
$\beta = 0.90$	Probability of Type II error: power = $1 - \beta$
$p_{C} = p_I = 0.95$	Estimated success rate for control and treatment groups
δ = 0.08	Non-inferiority Margin

Resulting sample sizes (number of knees), not adjusted for attrition, are 191 Cementless device vs. 96 Control (5% type I error rate, 90% power). We increase our sample size by 10% to allow for possible exclusions in the primary analysis due to bilateral patients who may not be poolable with the unilateral cases, as well as attrition of up to 15%. This gives a sample size of 383 total subjects (255 Cementless vs. 128 Control).

